0.2	15Mar2018	[REDACTED]	Revise 3.1 section according to protocol version 2 Revise the REAS according to protocol version 2 Add the FAS according to the requirement for analysis Delete the shift table for low, high, normal according to protocol
0.3	24Jan2019	[REDACTED]	Add the definition of OS and PFS at 12 weeks Revise the population set of REAS to EAS. Add the definition of subsequent anti-cancer therapy. Delete the shift from baseline analysis of ECOG PS. Global changes according to protocol version 3.
1.0	30Jan2019	[REDACTED]	Upgrade version, no updates.
1.0	17Jan2020	[REDACTED]	Updating SAP & Shell according to sponsor' comments
1.1	11Feb2020	[REDACTED]	Updating SAP & Shell according to sponsor' comments
	03Mar2020	[REDACTED]	Update Table 14.1.1.1, Table 14.1.6.1, source listing of Table 14.1.6.2,
	09Mar2020	[REDACTED]	Update shell of " Listing 16.2.7.2"
	12Mar2020	[REDACTED]	Revise source listing of Table 14.1.3, update section 7.3
	16Mar2020	[REDACTED]	Update notes to programmer of Listing 16.2.7.3 Update layout of Listing 16.2.1.1, 16.2.1.2 and 16.2.6.5
	17Mar2020	[REDACTED]	Updating Source of Table 14.1.2 and notes to programmer of Listing 16.2.9.1.1

Document: [REDACTED]

Author: [REDACTED]

Version Number:

2.5

Version Date:

18Feb2022

Template No.: [REDACTED]

Reference: CS_WI_BS005

Effective Date: 02Dec2019

	07Apr2020		
 - Updating Listing 16.2.1.2, 16.2.3.1, 16.2.4.2, 16.2.5.1.1, 16.2.5.2, 16.2.5.1.3, 16.2.5.6, 16.2.7.2, 16.2.6.4, 16.2.7.7; Table 14.1.4.3.2, 14.3.1.2, 14.3.1.3.2 - Updating footnote of Listing 16.2.4.2, 16.2.5.1.2, 16.2.5.2, 16.2.5.3; Table 14.3.1.6.2, 14.3.1.7.3, 14.3.1.8.3, - Updating note to programmer of Table 14.3.1.11.3, 14.3.1.12.3, - Typo: Listing 16.2.4.2, 16.2.5.1.2, - Revision of table caption: 14.2.1.1, 14.2.2.1, 14.2.3.1, 14.2.4.1, 14.2.5.1 - Adding Table 14.2.1.2, 14.2.2.2, 14.2.3.2, 14.2.4.2, 14.2.5.2, 14.4.1, 14.4.2 - Adding Figure 14.2.1.2, 14.2.2.2, 14.2.3.2, 14.2.4.2, and 14.4.1 - SAP update: 18.2.1
1.2	15Oct2020		
 - Revision done for amended protocol V.4.0 -Wording change on replacing ‘subject’ with ‘patient’ -Typos -Output Conventions -Revisions were done in almost all sections except for section 4.2, 6, 7.1, 7.2, 7.3.3-7.5, 8, and 14.
2.0	23Nov2020		Revision according to sponsor’s comments
	30Nov2020		
 - Revisions of format and typos - Remove one blank page

ECOG PS	Eastern Cooperative Oncology Group Performance Status
eCRF	Electronic Case Report Form
ENR	All Patients Enrolled Set
HR	Hormone Receptor
INR	International Normalized Ratio
LLQ	Lower Limit of Quantification
mCRC	Metastatic Colorectal Cancer
MedDRA	Medical Dictionary for Regulatory Activities
MUGA	Multi-Gated Acquisition
NCI	National Cancer Institute

Document:

Author:

Version Number:

2.5

Version Date:

18Feb2022

Template No.:

Reference: CS_WI_BS005

Effective Date: 02Dec2019

NCS	Not Clinically Significant
NE	Not Evaluable
NSCLC	Non-Small Cell Lung Cancer
ORR	Objective Response Rate
OS	Overall Survival
PD	Progressive Disease
PFS	Progressive Free Survival
PID	Percentage Intended Dose
PLT	Blood platelet count
PR2D	Recommended Phase 2 Dose
PR	Partial Response
RD	Relative Dose
PT	Preferred Term
QD	Quaque Die/ Once Daily
RDI	Relative Dose Intensity
RECIST	Response Evaluation Criteria in Solid Tumors
SAE	Serious Adverse Event
SAP	Statistical Analysis Plan
SAS	Safety Analysis Set
SD	Stable Disease
SMQ	Standardized MedDRA Queries
SOC	System Organ Class
STD	Standard Deviation
TEAE	Treatment-Emergent Adverse Event
TEAESI	Treatment-Emergent Adverse Event of Special Interest
TNBC	Triple-Negative Breast Cancer
TSH	Thyroid stimulating hormone
ULN	Upper Limit of Normal
ULQ	Upper Limit of Quantification
VEGF	Vascular Endothelial Growth Factor
WHO DDE	World Health Organization Drug Dictionary Enhanced

Document: [REDACTED]

Author: [REDACTED] Version Number: 2.5
 Version Date: 18Feb2022

Template No.: [REDACTED] Reference: CS_WI_BS005

Effective Date: 02Dec2019

1. INTRODUCTION

This document describes the rules and conventions to be used in the presentation and analysis of efficacy and safety data for Protocol 2015-013-00US1. It describes the data to be summarized and analyzed, including specifics of the statistical analyses to be performed.

This statistical analysis plan (SAP) is based on protocol Version 4.0 (Amendment 4), dated 09 Jan 2020. The Pharmacokinetics (PK) and pharmacodynamics analyses will not be performed by IQVIA Biostatistics (BIOS) and therefore are not documented in this SAP.

1.1. PRIMARY OBJECTIVE

1.1.1. DOSE ESCALATION PHASE

The primary objective of the dose escalation phase is to evaluate the safety and tolerability of fruquintinib in patients with advanced solid tumors and to determine the recommended Phase 2 dose (RP2D).

1.1.2. DOSE EXPANSION PHASE

The primary objective of the dose expansion phase is to evaluate the anticancer activity of fruquintinib at the recommended RP2D from the dose escalation phase, in patients with advanced solid tumors.

1.2. SECONDARY OBJECTIVES

1.2.1. DOSE ESCALATION PHASE

The secondary objectives of the dose escalation phase are:

- To evaluate the PK characteristics of multiple dose fruquintinib and to investigate the metabolite profile of fruquintinib in the plasma of patients with solid tumors (The detailed analysis method will not be documented in this document).
- To evaluate anticancer activity of fruquintinib in patients with solid tumors according to the Response Evaluation Criteria in Solid Tumors (RECIST) Version 1.1 (Eisenhauer et al., 2009).

1.2.2. DOSE EXPANSION PHASE

The secondary objectives of the dose expansion phase are:

- To evaluate anticancer efficacy of fruquintinib, as assessed by Objective response rate (ORR), disease control rate (DCR), duration of response (DoR), progression free survival (PFS) and overall survival (OS).
- To evaluate the PK characteristics of multiple dose fruquintinib and to investigate the metabolite profile of fruquintinib in plasma.
- To evaluate the safety of fruquintinib.

Document: [REDACTED]

Author: [REDACTED]

Version Number: 2.5

Version Date: 18Feb2022

[figure not shown]
Template No.: [REDACTED]

Reference: CS_WI_BS005

Effective Date: 02Dec2019

2. STUDY DESIGN

The study is an open-label phase 1/1b study of fruquintinib comprised of a dose escalation phase that will enroll patients with advanced solid tumors of any type, and a dose expansion phase that will enroll patients with advanced solid tumors of any type (Cohort A) and in patients with refractory metastatic colorectal cancer (mCRC, Cohort B and C), or breast cancer (BC, Cohort D and E) (see study schema below).

Approximately 128 patients will be enrolled in this dose escalation/dose expansion study. Approximately 12 patients will be enrolled in the dose escalation phase, and approximately 116 additional patients (6 with advanced solid tumors of any type and 40 with refractory mCRC who progressed on TAS-102 and/or regorafenib, 40 with mCRC who had not received TAS-102 or regorafenib, 15 with refractory HR+/HER2- mBC, and 15 with advanced, refractory triple-negative breast cancer (TNBC) will be enrolled in the dose expansion phase.

2.1. DOSE ESCALATION PHASE

Approximately 12 evaluable patients will be enrolled. The actual number of patients will depend on the occurrence of dose-limiting toxicities (DLTs) as well as the Maximum Toxicity Dose (MTD) level reached in this trial. MTD is the highest dose at which no more than 1 of the 6 patients in each cohort of the dose escalation phase develops a DLT. If 2 or more of 6 patients in each cohort of the dose escalation phase develop DLT at a particular dose level, that dose has exceeded the MTD. The dose levels to be investigated are 3 mg and 5 mg once daily (QD), 3 weeks on/1 week off.

Document: [REDACTED]

Author: [REDACTED] Version Number: 2.5

Version Date: 18Feb2022

Template No.: [REDACTED] Reference: CS_WI_BS005

Effective Date: 02Dec2019

The definition of DLTs and the DLT assessment window is provided in [section 17.1](#) and the definition of a DLT evaluable patient is provided in [section 4.3](#).

To investigate DLT, 6 DLT-evaluable patients will be firstly enrolled in the phase and will be treated with fruquintinib 3 mg QD (3 weeks on/ 1 week off) orally. If no more than 1 DLT occurs during the DLT observational window (i.e. from Day 1 – 28 in Cycle 1) among the 6 patients, the trial will continue to enroll another 6 patients in the next dose cohort in which fruquintinib 5 mg QD (3 weeks on / 1 week off) will be tested. Safety monitoring and evaluation for the dose escalation phase will be carried out by the Safety Review Committee (SRC). If no more than 1 patient at the dose level of 5 mg QD experiences a DLT, the dose escalation phase is completed, and the expansion phase of the study will be conducted. Upon the completion of the dose escalation phase, the SRC will review aggregated safety and PK data and then select a fruquintinib dose as the RP2D for the expansion phase of the trial. Prior to confirmation of a DLT, if a patient has received any prophylactic medical intervention or missed 4 or more fruquintinib dose during the DLT observational window, the patient is not DLT evaluable and will be replaced. If a patient does not meet the definition of DLT evaluable patient criterion during the DLT observation period, the patient will be replaced. Patients who have completed the DLT observation period (Days 1 – 28, Cycle 1) and are deemed to be benefiting from the fruquintinib treatment at the investigator’s discretion may continue the fruquintinib treatment until disease progression, death, intolerable toxicity, or at investigator’s discretion that the patient can no longer benefit from the study drug.

Patients will be followed until death or study completion, which is defined as the CRF form “End of Study” is filled.

2.2. DOSE EXPANSION PHASE

Once the RP2D is determined, patients may enroll into one of the following cohorts and will receive fruquintinib at the RP2D.

- Cohort A: Patients with advanced, refractory solid tumors of any type.
- Cohort B: Patients with refractory mCRC who have progressed on all standard chemotherapies and relevant biologics and have also progressed on, or had intolerable toxicity with, at least 1 FDA-approved third-line therapy (TAS-102 or regorafenib).
- Cohort C: Patients with refractory mCRC who have progressed on all standard chemotherapies and relevant biologics and have not received prior TAS-102 or regorafenib.
- Cohort D: Patients with hormone-receptor positive (ER+ and/or PR+)/Her2-metastatic breast cancer who have progressed on at least two line of prior systemic therapy.
- Cohort E: Patients with advanced TNBC who have progressed on at least one cytotoxic therapy in the metastatic setting

Document: [REDACTED]

Author: [REDACTED] Version Number: 2.5
 Version Date: 18Feb2022

Template No.: [REDACTED] Reference: CS_WI_BS005

Effective Date: 02Dec2019

The safety of all enrolled patients will be closely monitored from the first day of fruquintinib dosing until 30 days after the last dose. All serious adverse events (SAEs) should be reported from the day the informed consent form (ICF) is signed through 30 days after last dose regardless of relationship to study drug. All AEs will be graded in accordance with the National Cancer Institute (NCI) Common Terminology Criteria for Adverse Events (CTCAE) V4.03.

In the dose expansion phase, tumor response will be assessed according to RECIST Version 1.1 (Eisenhauer et al., 2009) at screening, and at study visits according the Schedule of Events (Appendix A in the protocol). Confirmation of complete response (CR) and partial response (PR) is required at no less than 4-week intervals between the date of initial response and the confirmation assessment date.

Patients will be followed until death or study completion.

2.3. STUDY ENDPOINTS

2.3.1. DOSE ESCALATION PHASE

- Primary Endpoints: The primary endpoint of the dose escalation phase is the incidence of DLT in each cohort.
- Secondary endpoints: The objective response rate (ORR), disease control rate (DCR), duration of response (DoR), and progression free survival (PFS) according to RECIST Version 1.1 (Eisenhauer et al., 2009), overall survival (OS) and percentage change from baseline in tumor size.

2.3.2. DOSE EXPANSION PHASE

- Primary endpoint: PFS
- Secondary endpoints:
 - Efficacy analysis: ORR, DCR, DoR, PFS according to RECIST Version 1.1 (Eisenhauer et al., 2009), OS and percentage change in tumor size from baseline.
 - Safety analysis: the incidence and severity of adverse events (AEs), physical examinations, vital signs, laboratory test results, 12-lead electrocardiogram, and echocardiogram.

Document: [REDACTED]

Author: [REDACTED] Version Number: 2.5
 Version Date: 18Feb2022

Template No.: [REDACTED] Reference: CS_WI_BS005

Effective Date: 02Dec2019

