Efficacy	
All patients from the safety analysis set who have at least one post-baseline tumor assessment will be included in the efficacy analysis set (EAS).
 
The ORR and DCR will be summarized by dose cohort with percentages and 95% exact confidence intervals for the EAS. The PFS rate at specific time points (eg, PFS rate at 12 weeks for Cohort C) and its 95% confidence interval will be estimated using the Kaplan-Meier method. PFS, DoR, and OS will be summarized descriptively using Kaplan-Meier medians and quartiles for patients in the SAS. Percentage change in tumor size will be determined for patients with measurable disease at baseline and will be derived at each visit by the percentage change in the sum of the diameters of target lesions (TLs) compared to baseline. The best percentage change in tumor size will be summarized using descriptive statistics and presented using a waterfall plot.

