### **2.2.2 Primary Endpoint**

The primary endpoint is PFS rate.

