## 8.5 Efficacy Analysis

The efficacy endpoints include PFS, ORR, DCR, and OS. Efficacy data will be listed and summarized by dose cohort and disease type.

The ORR and DCR will be summarized with percentages and 95% exact confidence intervals. The PFS rate at week 12 (Cohorts B and C) and week 16 (Cohorts D and E) and its 95% confidence intervals will be estimated by the Kaplan-Meier method. PFS, DoR, and OS will be summarized descriptively using Kaplan-Meier medians and quartiles. Percentage change in tumor size from baseline will be determined for patients with measurable disease at baseline and derived at each visit by the percentage change in the

sum of the diameters of target lesions (TLs) compared to baseline. Best percentage change in tumor size will be summarized using descriptive statistics and presented using a waterfall plot.

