### **Progression Free Survival (PFS)**

Progression free survival is defined as the time from date of first dose of study drug until the date of an objective disease progression as defined by RECIST v1.1 or death due to any cause.

Patients who have not objectively progressed or died by the date of the analysis cut-off or received any further antitumor therapy will be censored at the time of the last evaluable objective tumor assessment before the cut-off date or the antitumor therapy start date.

Progression-free survival rate is defined as the percentage of patients without evidence of progression or death at specific time points, such as week 12 (cohorts B and C), week 16 (cohort D and E) on study.

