16.2. ANALYSIS OF EFFICACY VARIABLE(S)

The efficacy endpoints include ORR, DCR, DoR, PFS and OS. Efficacy data will be listed and summarized by dose cohort (only in dose escalation phase) or tumor specific cohorts (only in dose expansion phase) and disease type if applicable.

ORR, DCR, and DoR

The ORR and DCR will be summarized with percentages and 95% exact Clopper-Pearson confidence interval based on EAS.

DOR will be summarized using Kaplan-Meier method, and the descriptive statistics of median, 25% and 75% percentiles along with their 95% CIs will be calculated. It will be based on the EAS. The supportive data listings will also be provided.

PFS, OS, and Duration to Follow-Up

PFS and OS will be similarly summarized as DOR, and in addition to the quartile summary from Kaplan-Meier method, Kaplan-Meier estimates will be provided for the rates at 12, 16, 20, and 24 weeks along with their 95% CIs based on the Brookmeyer and Crowley method (1982).

In addition, duration (months) to follow-up for overall survival would be summarized by Kaplan-Meier method. Duration to follow-up refers to the time interval between date of first study drug administration and last date known to be alive for subjects who have not yet been reported to have died by the time of analysis, i.e. (date of last known to be alive – date of first study drug administration + 1)/ 30.475. Subjects who are reported to have died would be censored at death date.

Tumor Shrinkage

Document: [REDACTED]

Author: [REDACTED] Version Number: 2.5
Version Date: 18Feb2022

Template No.: [REDACTED] Reference: CS_WI_BS005

Effective Date: 02Dec2019

Percentage change in tumor size from baseline will be determined for patients with measurable disease at baseline and derived at each visit by the percentage change in the sum of the diameters of target lesions (TLs) compared to baseline. Best (minimum) percentage change from baseline (PCFB) in tumor size will be summarized using descriptive statistics and a waterfall plot will be presented also. Best post-baseline sum of diameter is defined as the sum of diameter with either the largest decrease or smallest increase from baseline sum of diameter at a single post-baseline evaluable tumor assessment visit before RECIST progression of disease. More details please refer to [section 16.1.7](#).

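### The SAP names PFS, not the protocol's PFS rate, as the expansion-phase primary endpoint, and marks no landmark week as primary

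*SAP*

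**What the plan says.** **Protocol.** Section 2.2.2 states "The primary endpoint is PFS rate" and gives no week. Section 2.2.4 lists PFS separately as a secondary endpoint, so the protocol treats the rate and the time as two endpoints. Section 8.5 supplies the weeks in two places. Its analysis paragraph names "The PFS rate at week 12 (Cohorts B and C) and week 16 (Cohorts D and E", to be estimated by Kaplan-Meier with a 95% confidence interval. Its definition reads "Progression-free survival rate is defined as the percentage of patients without evidence of progression or death at specific time points", followed by "such as week 12 (cohorts B and C), week 16 (cohort D and E) on study". The synopsis offers only an example, "PFS rate at 12 weeks for Cohort C". No week is given for Cohort A.

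**SAP.** Section 1 says the SAP is based on protocol Version 4.0. Section 2.3.2 gives "Primary endpoint: PFS" for the expansion phase and, under secondary endpoints, "Efficacy analysis: ORR, DCR, DoR, PFS according to RECIST Version 1.1". Section 16.1.5 defines PFS only as a time from first dose. For PFS and OS alike, section 16.2 says "Kaplan-Meier estimates will be provided for the rates at 12, 16, 20, and 24 weeks", with no link between week and cohort. Section 2.4, on changes from the protocol, mentions PFS only in connection with the analysis set.

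**The concern.** A SAP should carry the protocol's primary endpoint forward or declare that it has changed. Here the primary line names a different variable from the governing protocol, the same variable is also secondary, and the list of changes is silent.

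This matters because the trial is open-label, and SAP 3 and 3.1 allow accrued data from any cohort to be analysed for internal decisions or external disclosure. With no landmark designated, the result put forward for a cohort could be the median or any of four rates, picked once the curve is known. Protocol 8.6 also justifies the cohort sizes by the precision of a proportion, including a PFS rate at a given time. It states no precision for a time-to-event primary.

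**Working it through.** **1. Does anything else in the SAP restore the designation?**
- Section 16.1 is headed as covering the primary efficacy variables, but it holds BOR, ORR, DoR, DCR, PFS, OS and tumor shrinkage together, so it singles out none.
- Section 16.1.5 defines no PFS rate.
- Section 16.2 contains weeks 12 and 16, but as two of four unranked weeks.
- Section 2.4 lists no endpoint change.

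So the estimates survive, but their status as primary, by cohort, does not.

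**2. The plan's own precision figures.** Protocol 8.6 states ±16% to 28% for N=15 and ±7% to 16% for N=40. The Clopper-Pearson limits are: lower = Beta⁻¹(0.025; x, n−x+1), upper = Beta⁻¹(0.975; x+1, n−x).
- 3/15: 0.043 to 0.481, at distances 0.157 and 0.281 from the estimate.
- 4/40: 0.028 to 0.237, at distances 0.072 and 0.137.
- 20/40: 0.338 to 0.662, at distance 0.162 on each side.

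Every limit in Tables 15 and 16 reproduces to two decimals. Leaving out the 0% and 100% rows, the stated ranges reproduce as well. No figure is wrong, and naming a landmark changes no sample size.

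**3. How far apart are the four rates?** The plan gives no expected PFS curve, so this is an illustration. Assume exponential PFS with median m months: S(w) = exp[−ln 2 × (7w/30.4375)/m]. The medians are those quoted in protocol 1.3.3: the fruquintinib arm of the phase 3 mCRC study (3.71), the fruquintinib arm of the phase 2 mCRC study (4.731), and the phase 3 placebo arm (1.84).

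| m | Week 12 | Week 16 | Week 20 | Week 24 | Week 12 minus week 24 |
|---|---|---|---|---|---|
| 3.71 | 59.7% | 50.3% | 42.3% | 35.7% | 24.0 points |
| 4.731 | 66.7% | 58.3% | 51.0% | 44.5% | 22.2 points |
| 1.84 | 35.4% | 25.0% | 17.7% | 12.5% | 22.9 points |

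At m = 3.71 with N=40 and no censoring, the nearest whole counts are 24/40 at week 12 (95% CI 43% to 75%) and 14/40 at week 24 (21% to 52%).

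**4. Scan timing.** Under protocol 6.4, Cohort C is scanned every 8 weeks. Its week-12 rate therefore falls between the first and second scheduled on-treatment scans, while week 16 coincides with the second. The two weeks rest on different amounts of imaging, which is a further reason to fix the choice in advance.

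**5. Interval method.** SAP 16.2 attaches the intervals for these rates to Brookmeyer-Crowley. The SAP's own reference list gives that as an interval for the median survival time, so no suitable method is named for the quantity the protocol makes primary.

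**The case against.** The case on the other side has real weight.

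- **The protocol is loose.** Its endpoint section has no week, the definition in 8.5 introduces the weeks as examples, and Cohort A has none. Only the analysis paragraph of 8.5 maps weeks to cohorts without qualification, and it does not call them primary. A single primary week per cohort comes from reading 2.2.2 and 8.5 together. This stands. It makes designation in the SAP more necessary, but the gap is partly inherited.
- **The word for rate may simply have been dropped.** A secondary PFS entry mirrors protocol 2.2.4, so a drafting slip is plausible. A reader might infer that the sponsor deliberately replaced the landmark with PFS time. The SAP does not say so. As written, though, it does not name the protocol's primary endpoint.
- **Nothing planned is lost.** Weeks 12 and 16 are reported for every cohort, and the mapping in protocol 8.5 remains available as a check. This stands.
- **No error rate is at stake.** A reader might count four rates plus a median in four cohorts, 20 summaries against 4, and see a multiplicity problem. SAP 5.5 tests no hypothesis, and these are correlated summaries of one curve per cohort, so the count measures neither error nor harm.
- **The spread is not bias.** The rates in the table fall because survival falls with time, and each estimates a different quantity. They show that the week matters to the headline figure. They do not show that anyone will select it.

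**Conclusion.** The mismatch is real and undeclared. The protocol's expansion primary is a rate; the SAP's is PFS without week or cohort, and its four landmarks are unranked. The consequence is limited to freedom to choose the headline summary after seeing the data, in an open-label study whose accrued cohort data may be disclosed. Sample size, power and type I error are untouched.

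The spread of roughly 22 to 24 percentage points between weeks 12 and 24 rests on an assumed exponential curve and on medians from other mCRC studies, so it says little about the breast cancer cohorts. The finding itself does not depend on it, because it follows from the text alone. This should be fixed. It is not grounds for doubting the study's design.

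**What to change.** - **SAP 2.3.2:** state that the primary endpoint is the Kaplan-Meier PFS rate, at week 12 in Cohorts B and C and at week 16 in Cohorts D and E. The sponsor should confirm the Cohort E week while editing: the amendment summary mentions week 24, which is not counted here as an error because it is log text. Say what applies to Cohort A, for example descriptive reporting only.
- **SAP 16.2:** label those estimates as the primary analysis, and label the other landmarks and the median as secondary. For the landmark rates, replace Brookmeyer-Crowley with a method meant for a Kaplan-Meier rate at a fixed time, such as Greenwood's variance with a log-log transformation. Brookmeyer-Crowley can stay for the median.
- **If PFS time really is meant to be primary:** say so, with the reason, in SAP 2.4.

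The cost is a few sentences and one interval setting in the programs. It needs no new data, no new landmark estimates and no change in sample size.
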